## 2.0 Inclusion and Exclusion Criteria

- 2.1 *Describe the criteria that define who will be included or excluded in your final study sample.*

### Characteristics of the Research Population

- Gender of Subjects: Male and female subjects
- Age of Subjects: 15 – 21 years
- Racial and Ethnic Origin: All racial and ethnic groups will be included
- Inclusion Criteria
  - Adolescents and young adults followed by the UBMD Pediatrics, Division of Endocrinology/Diabetes Center.
  - Diagnosis of T1DM greater than 1 year
  - Insulin regimen – continuous subcutaneous insulin infusion with or without concurrent use of continuous glucose monitoring device
  - HbA1c <10%
- Exclusion Criteria
  - Previous exposure to liraglutide
  - History of abdominal surgery
  - Gastrointestinal reflux disease
  - History of acute or chronic pancreatitis
  - History of alcohol abuse or unwillingness to abstain from alcohol during the study
  - Unwilling to wear a continuous glucose monitoring device during the study.
  - History of thyroid cancer
  - Family history of Multiple Endocrine Neoplasia 2B syndrome
  - Pregnant/breastfeeding females
  - Individuals with antibody-negative insulin requiring diabetes that is consistent with Monogenic Diabetes of Youth
  - Individuals with steroid induced or cystic fibrosis related diabetes.
  - Non-English speaking subjects

- 2.2 *Describe how individuals will be screened for eligibility.*

*Response:*

**Recruitment:** Subjects will be recruited from the UBMD Pediatrics, Division of Endocrinology/Diabetes clinic.

- 2.3 *Indicate specifically whether you will include or exclude each of the following special populations: (You may not include members of these populations as subjects in your research unless you indicate this in your inclusion criteria.)*

- *Adults unable to consent*
- *Individuals who are not yet adults (infants, children, teenagers)*
- *Pregnant women*
- *Prisoners*

Response: N/A

- 2.4 *Indicate whether you will include non-English speaking individuals. Provide justification if you will exclude non-English speaking individuals.*

*(In order to meet one of the primary ethical principles of equitable selection of subjects, non-English speaking individuals may not be routinely excluded from research. In cases where the research is of therapeutic intent or is designed to investigate areas that would necessarily require certain populations who may not speak English, the researcher is required to make efforts to recruit and include non-English speaking individuals. However, there are studies in which it would be reasonable to limit subjects to those who speak English: e.g., pilot studies, small unfunded studies with validated instruments not available in other languages, numerous questionnaires, and some non-therapeutic studies which offer no direct benefit.)*

Response: We will not be including non-English speaking individuals in this study for the following reasons 1) pilot study; 2) unfunded

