### **Variables of Interest:**

#### **Visit 1**

- Age, gender, height, weight, total daily insulin dose, HbA1c, insulin pump settings
- Total daily insulin dose
- History of severe hypoglycemic events,
- History of pancreatitis, alcohol use, thyroid cancer, family history of MEN 2B

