#### **Visit 1 Screening Day (day 0):**

- Review the subject's medical history and family medical history
- Review subject's blood sugars and insulin pump settings
- Measure height, weight, blood pressure and heart rate.
- The principal investigator will perform a physical exam.
- If hemoglobin A1c level is not recorded in the medical record within 2 weeks of visit 1, this test will be performed.
- Record mean total daily insulin dose (previous 72 hours) from insulin pump.
- Subjects will be advised to wear his/her continuous glucose monitor (CGM) for the next two weeks, changing sites as indicated by the manufacturer.
- For subjects who do not have a CGM, we will insert the Abbott Freestyle Libre Professional Device. This device will monitor glucose levels throughout the entire study period. Subjects will be advised to check blood sugars at least 4 times per day and at any occasion when symptoms of hypoglycemia develop.
- Subjects will be asked to keep a record of any episodes of hypoglycemia.
- Subjects will be asked to keep a 4 day food record (three days, 1 weekend day).
- Subjects will be advised to follow their usual diabetes care plan with respect to carbohydrate counting, diet and exercise.

**Visit 2 (Day 7):** Subjects will come fasting for this visit. They will bring the food records and diary of hypoglycemia to this visit. This visit will take approximately 4 hours. At this visit, the following procedures will be performed:

- Records of blood sugars and CGM data will be obtained from subjects wearing personal CGMs
- Subjects wearing the Freestyle LibrePro system will continue wearing the device unless it became dislodged during the study. A new device will be placed in this case.
- Blood sugars and insulin pump settings will be reviewed.
- Record mean total daily insulin dose (previous 72 hours) from insulin pump.
- A Mixed Meal Tolerance test will be performed (see below)

- Insulin pump settings will be adjusted to decrease the risk of hypoglycemia during liraglutide treatment. Basal rates will be decreased by 25% and meal boluses will be decreased by 33%.
- The first dose of liraglutide will be given at the study site. Subjects will be given 0.6 mg subcutaneously. Subjects will be taught how to use the delivery device at this visit.
- Subjects will be advised to take 0.6 mg of liraglutide subcutaneously every morning at about the same time.

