**Response: Types of Risk:**

**Important Safety Information (see attached product information):** In animal studies, liraglutide caused rats and mice to develop thyroid tumors, some of which were cancers. It is not known whether liraglutide causes thyroid tumors or a type of thyroid cancer called medullary thyroid cancer in humans. Subjects with a history or family history of medullary thyroid cancer or Multiple Endocrine Neoplasia syndrome type 2 (MEN2) will not be enrolled in this study.

Treatment with GLP-1 is associated with inflammation of the pancreas (pancreatitis) which may be severe and can lead to death. Certain conditions increase the risk of developing pancreatitis including history of pancreatitis, gallstones, alcoholism, or high triglyceride levels. We will review the subject's medical record to assess for any of these risk factors. In addition, subjects will be excluded if they have a history of pancreatitis. While taking liraglutide, the subjects will be counseled to notify study staff if they develop severe abdominal pain. Should this occur, they will be advised to discontinue liraglutide and testing for pancreatitis will be performed (serum amylase and lipase). Subjects will also be counseled not to consume alcohol while enrolled in this study.

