## 18.0 Setting

*18.1 Describe the sites or locations where your research team will conduct the research.*

Response: The research will be conducted at the UBMD Pediatrics, Division of Endocrinology/Diabetes clinic space at [name]. All study testing will be done in a designated private and quiet area. For some subjects, Visits 2 and 3 will take place at the [name].

*18.2 Identify where your research team will identify and recruit potential subjects.*

*Response:* The research team will identify potential subjects at their clinic visit at the Diabetes Center . During visit 1, eligibility for the study will be determined. The study protocol will be reviewed with the subject and parent/guardian. Informed consent will be signed by the parent/guardian or subject (age $\geq$  18 years) with assent provided by subjects under 18 years of age. Subjects will be provided copies of the consent/study protocol and will be advised to notify study staff if they choose not to participate in the study. Signed consents will be stored in a locked file cabinet in the PI’s locked office. Subjects will be provided with copies of signed consents.

*18.3 Identify where research procedures will be performed.*

Response: All research procedures will be performed in a designated private and quiet research area in the UBMD Pediatrics, Division of Endocrinology/Diabetes clinic space at [name]. For some subjects, Visits 2 and 3 will take place at the [name].

*18.4 Describe the composition and involvement of any community advisory board.*

Response: N/A

*18.5 For research conducted outside of the organization and its affiliates describe:*

- *Site-specific regulations or customs affecting the research for research outside the organization.*
- *Local scientific and ethical review structure outside the organization.*

Response: N/A

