## **22.0 Local Number of Subjects**

*22.1 Indicate the total number of subjects to be accrued locally.*

Response: 12

*22.2 If applicable, distinguish between the number of subjects who are expected to be enrolled and screened, and the number of subjects needed to complete the research procedures (i.e., numbers of subjects excluding screen failures.)*

Response: We expect that all subjects who meet inclusion/exclusion criteria and sign informed consent/assent will complete the study.

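### The exclusion list omits three thyroid-cancer and MEN2 histories that the risk section says bar enrolment, so a barred subject could pass the eligibility criteria

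*Combined protocol and SAP*

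**What the plan says.** Section 13.1 (Risks to Subjects, Important Safety Information) reports thyroid tumours in rats and mice given liraglutide and says it is not known whether the drug causes them in humans. It then states the rule: "Subjects with a history or family history of medullary thyroid cancer or Multiple Endocrine Neoplasia syndrome type 2 (MEN2) will not be enrolled".

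The exclusion criteria in section 2.1 contain two related items: "History of thyroid cancer" and "Family history of Multiple Endocrine Neoplasia 2B syndrome". The list words personal and family history as separate items, so the thyroid item reads as personal history only.

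The Visit 1 entry under Variables of Interest in section 7.1 has the same scope as the list: "History of pancreatitis, alcohol use, thyroid cancer, family history of MEN 2B". The Visit 1 procedures in section 8.2 add a general step, "Review the subject's medical history and family medical history", which names no thyroid or MEN item and gives no exclusion rule.

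On how eligibility is decided, section 18.2 says "During visit 1, eligibility for the study will be determined".

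**The concern.** The protocol gives two different rules for who is kept out on thyroid grounds, and the narrower one stands where eligibility is normally read. The prompt that opens section 2.1 asks the investigator to "Describe the criteria that define who will be included or excluded in your final study sample". Staff who screen from that list, and record the history items in section 7.1, would find no reason to turn away a candidate whose parent had MTC. Enrolling that candidate would satisfy section 2.1 and breach section 13.1.

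What is at stake is subject safety and a clear eligibility rule. Candidates may be as young as 15, and liraglutide is not approved for type 1 diabetes. Sample size, power and alpha are not affected.

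**Working it through.** **Comparison of the two rules.** Section 13.1 names two conditions (MTC, MEN2), each as personal or family history, which makes four categories.

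| Category barred in 13.1 | Exclusion list, 2.1 | Left uncovered |
|---|---|---|
| Personal MTC | Covered, through thyroid cancer of any type | Nothing |
| Family MTC | Not named | All |
| Personal MEN2 | Only if thyroid cancer has already occurred | Personal MEN2 without thyroid cancer |
| Family MEN2 | Subtype 2B only | Family MEN2 other than 2B |

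One category is covered fully, two partly and one not at all, which leaves three uncovered groups. The Visit 1 variables in section 7.1 leave the same three.

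In one respect the list is the stricter text: it excludes every thyroid cancer, where section 13.1 names only medullary. That closes none of the gaps.

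**Other places that might close the gap.**
- Section 2.2 asks how subjects are screened; the answer gives only the recruitment source.
- Section 21.3 identifies candidates by diabetes duration and pump use.
- Section 8.5 lists the data items to be collected and includes no thyroid or family history item.
- The medical-record check in section 13.1 concerns risk factors for pancreatitis.

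None of these reconciles the two versions.

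**Exposure of a subject enrolled in error.** Under section 8.2 the first dose is given at Visit 2 (Day 7), dosing is every morning, and the last dose is given at Visit 3 (Day 14).
- Doses: 14 − 7 + 1 = 8
- Total: 8 × 0.6 mg = 4.8 mg

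**Chance that it arises.** The documents give no prevalence for the unlisted histories, so *p* = 0.01% to 0.1% of candidates is an assumption made only to show scale. With 12 subjects (section 22.1), the chance of at least one is 1 − (1 − *p*)^12:
- *p* = 0.0001: 1 − 0.9999^12 = 0.0012, or 0.12%
- *p* = 0.001: 1 − 0.999^12 = 0.0119, or 1.2%

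These figures assume that nobody catches the history by another route, so under the assumed *p* they are upper values.

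**The case against.** The strongest reply is that the two texts can both be obeyed. The exclusion list does not permit anyone in the three groups to enrol; it only fails to name them, and section 13.1 bars them outright. Read as a whole, the protocol already excludes these people, so the fault is an incomplete list.

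There are also practical safeguards. Family history is reviewed at Visit 1, and the Visit 1 variables at least raise thyroid cancer and MEN. The principal investigator is a board-certified pediatric endocrinologist (19.1) who performs the Visit 1 examination (8.2), and study personnel must review the protocol (19.6). The data collection tool is an attachment not available here and may ask the right questions.

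The evidence that the section 2.1 list governs is also partly indirect. Its heading is the form's own prompt, and section 18.2 does not say that only this list is used. The statement in section 22.2 that "all subjects who meet inclusion/exclusion criteria and sign informed consent/assent will complete the study" is introduced as an expectation about completion, not as an enrolment rule.

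Much of this stands. Wrongful enrolment is possible rather than directed, careful staff could well prevent it, and what the unseen forms ask is unknown. But none of it corrects the list. A safety exclusion should not depend on screening staff recalling a sentence in the risk section when the criteria and the recorded variables both state something narrower.

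**Conclusion.** The concern holds. The written exclusion criteria would admit three groups that the protocol itself bars on safety grounds: family MTC, personal MEN2 without thyroid cancer, and family MEN2 other than 2B. This follows from the text alone and needs no outside source.

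The expected number affected is very small. The 0.12% to 1.2% range rests wholly on the assumed prevalence and on no other safeguard working. The case for correction rests on the conflict between a stated safety rule and the criteria meant to carry it out, not on expected counts. It should be corrected before subjects are screened.

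**What to change.** In the section 2.1 exclusion list, replace the MEN 2B item with: *Personal or family history of medullary thyroid cancer or MEN2 (any subtype)*. Keep the separate exclusion for any personal history of thyroid cancer. Put the same items in the Visit 1 variables in section 7.1, so that each is asked and recorded. Do not resolve the mismatch by narrowing section 13.1, which would weaken a protection already stated.

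The cost is wording in two places and a few questions at a visit that already reviews medical and family history. Recruitment is barely touched. Of the roughly 130 pump-treated patients in section 19.2, the same assumed prevalence implies 130 × 0.0001 = 0.013 to 130 × 0.001 = 0.13 additional ineligible candidates.

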### **3.0 Study-Wide Number of Subjects (Multisite/Multicenter Only)**

- 3.1 *If this is a multicenter study, indicate the total number of subjects to be accrued across all sites.*

Response: N/A

### **4.0 Study-Wide Recruitment Methods (Multisite/Multicenter Only)**

*If this is a multicenter study and subjects will be recruited by methods not under the control of the local site (e.g., call centers, national advertisements) describe those methods. Local recruitment methods are described later in the protocol.*

- 4.1 *Describe when, where, and how potential subjects will be recruited.*

Response: N/A

- 4.2 *Describe the methods that will be used to identify potential subjects.*

Response: N/A

- 4.3 *Describe materials that will be used to recruit subjects. (Attach copies of these documents with the application. For advertisements, attach the final copy of printed advertisements. When advertisements are taped for broadcast, attach the final audio/video tape. You may submit the wording of the advertisement prior to taping to preclude re-taping because of inappropriate wording, provided the IRB reviews the final audio/video tape.)*

Response: N/A

## 5.0 Multi-Site Research (Multisite/Multicenter Only)

5.1 *If this is a multi-site study where you are the lead investigator, describe the processes to ensure communication among sites, such as:*

- *All sites have the most current version of the protocol, consent document, and HIPAA authorization.*
- *All required approvals have been obtained at each site (including approval by the site's IRB of record).*
- *All modifications have been communicated to sites, and approved (including approval by the site's IRB of record) before the modification is implemented.*
- *All engaged participating sites will safeguard data as required by local information security policies.*
- *All local site investigators conduct the study appropriately.*
- *All non-compliance with the study protocol or applicable requirements will be reported in accordance with local policy.*

Response: N/A

5.2 *Describe the method for communicating to engaged participating sites:*

- *Problems.*
- *Interim results.*
- *The closure of a study*

Response: N/A

## 6.0 Study Timelines

6.1 *Describe the duration of an individual subject's participation in the study.*

Response: The total duration of time for participation is 2 weeks. This study involves three visits.

6.2 *Describe the duration anticipated to enroll all study subjects.*

Response: 4 years

6.3 *Describe the estimated date for the investigators to complete this study (complete primary analyses)*

Response: 60 months

## 7.0 Study Endpoints

7.1 *Describe the primary and secondary study endpoints.*

Response: For statistical purposes, the **primary endpoint** of the study is to detect a difference between untreated and treated periods in the change from baseline in mean weekly blood glucose concentrations. The statistical analysis will be carried out using

analysis of variance (ANOVA) and tested at the 0.05 level. The results will be computed as mean $\pm$ SD.

The secondary end points based on glycemic changes will include the difference from baseline in standard deviations of the mean weekly glucose concentrations, mean fasting blood glucose concentrations, the duration of time spent in hyperglycemia ( $>150\text{mg/dl}$ ,  $>200\text{mg/dl}$ ,  $>250\text{mg/dl}$ ) and hypoglycemia ( $<70\text{mg/dl}$ ,  $<40\text{mg/dl}$ ), and insulin dosage. A reduction in the area under curve following the meal will constitute another secondary end point. Within subject comparisons of the magnitude of change from baseline will also be made for these glycemia related secondary endpoints using student's t-test. Comparisons for these and the primary endpoints will also be made using the paired *t*-test or Wilcoxon's test for paired data for each subject. Additional secondary end-points of the study will be change from baseline in 1) mean weekly blood glucose 2) glucagon area under the curve concentrations following meal challenge 3) change in daily insulin dose (total dose and units/kg) 4) caloric intake based on 4 day food records and 5) change in serum adiponectin and CRP levels before and after initiation of liraglutide treatment. The relation between change in postprandial sugars, glucagon, and total daily insulin dose will be studied by regression analysis to evaluate the relative contribution of each of these parameters to the improvement in post-prandial blood sugars.

### **Variables of Interest:**

#### **Visit 1**

- Age, gender, height, weight, total daily insulin dose, HbA1c, insulin pump settings
- Total daily insulin dose
- History of severe hypoglycemic events,
- History of pancreatitis, alcohol use, thyroid cancer, family history of MEN 2B

#### **Visit 2**

- Insulin pump settings
- Total daily insulin dose
- Food diaries
- Download of continuous glucose monitor – mean weekly blood sugars
- Blood sugar records with reports of hypoglycemia
- Mean blood glucose excursion, glucagon release, and serum inflammatory markers during mixed meal tolerance test

#### **Visit 3**

- Insulin pump settings
- Total daily insulin dose
- Food diaries
- Download of continuous glucose monitor – mean weekly blood sugars
- Blood sugar records with reports of hypoglycemia
- Adverse effects
- Mean blood glucose excursion, glucagon release, and serum inflammatory markers during mixed meal tolerance test

*Describe any primary or secondary safety endpoints.*

**Response:** Adverse effects including nausea/vomiting, anorexia. Injection site reactions/pain. Rates of hypoglycemia. Clinical or biochemical evidence of pancreatitis.

## **8.0 Procedures Involved**

### *8.1 Describe and explain the study design.*

**Response:** This is a pilot unblinded prospective within subject investigational-drug intervention trial.

### *8.2 Provide a description of all research procedures being performed and when they are performed, including procedures being performed to monitor subjects for safety or minimize risks.*

**Response:**

#### **Summary of Research Design and Procedures:**

The proposed study will involve three visits. The study will involve an initial screening meeting at which time the subject will be invited to join the study and sign informed consent. During the Visit 2 and Visit 3, mixed meal tolerance tests will be performed.

#### **Visit 1 Screening Day (day 0):**

- Review the subject's medical history and family medical history
- Review subject's blood sugars and insulin pump settings
- Measure height, weight, blood pressure and heart rate.
- The principal investigator will perform a physical exam.
- If hemoglobin A1c level is not recorded in the medical record within 2 weeks of visit 1, this test will be performed.
- Record mean total daily insulin dose (previous 72 hours) from insulin pump.
- Subjects will be advised to wear his/her continuous glucose monitor (CGM) for the next two weeks, changing sites as indicated by the manufacturer.
- For subjects who do not have a CGM, we will insert the Abbott Freestyle Libre Professional Device. This device will monitor glucose levels throughout the entire study period. Subjects will be advised to check blood sugars at least 4 times per day and at any occasion when symptoms of hypoglycemia develop.
- Subjects will be asked to keep a record of any episodes of hypoglycemia.
- Subjects will be asked to keep a 4 day food record (three days, 1 weekend day).
- Subjects will be advised to follow their usual diabetes care plan with respect to carbohydrate counting, diet and exercise.

**Visit 2 (Day 7):** Subjects will come fasting for this visit. They will bring the food records and diary of hypoglycemia to this visit. This visit will take approximately 4 hours. At this visit, the following procedures will be performed:

- Records of blood sugars and CGM data will be obtained from subjects wearing personal CGMs
- Subjects wearing the Freestyle LibrePro system will continue wearing the device unless it became dislodged during the study. A new device will be placed in this case.
- Blood sugars and insulin pump settings will be reviewed.
- Record mean total daily insulin dose (previous 72 hours) from insulin pump.
- A Mixed Meal Tolerance test will be performed (see below)

- Insulin pump settings will be adjusted to decrease the risk of hypoglycemia during liraglutide treatment. Basal rates will be decreased by 25% and meal boluses will be decreased by 33%.
- The first dose of liraglutide will be given at the study site. Subjects will be given 0.6 mg subcutaneously. Subjects will be taught how to use the delivery device at this visit.
- Subjects will be advised to take 0.6 mg of liraglutide subcutaneously every morning at about the same time.
- Subjects will be given a diary and be asked to record any episodes of hypoglycemia, as well as any other side effects such as nausea, decrease in appetite, and other problems.
- Subjects will be asked to keep a 4 day food record (three days, 1 weekend day).
- Subjects will be provided with contact information for the principal investigator in case of any problem or untoward side effect. They will be asked to notify the study staff for persistent low blood sugar (BS < 70 mg/dL), persistent high blood sugar (BS > 250 mg/dL), or urine ketones.
- Subjects will be advised to return to clinic in 7 days.

**Visit 3 (Day 14):** This is the final study visit. Subjects will come fasting for this visit. The subject will not take liraglutide prior to coming to this visit but will bring the study drug to the visit. Subjects will bring the food records and diary of hypoglycemia to this visit. This visit will take approximately 4 hours. At this visit, the following procedures will be performed:

- Records of blood sugars and CGM data will be obtained.
- Freestyle LibrePro device will be removed and data obtained.
- Blood sugars and insulin pump settings will be reviewed
- Record mean total daily insulin dose (previous 72 hours) from insulin pump.
- Liraglutide (0.6 mg subcutaneously) will be administered 45 minutes prior to the Mixed Meal Tolerance Test
- A Mixed Meal Tolerance test will be performed (see below).
- All study drug will be returned.
- Subjects will be advised to resume previous basal rates and carbohydrate ratios within 48 hours of final study visit.

**Mixed Meal Tolerance Test (MMTT).** This test will be done at Visit 2 and Visit 3. The MMTT is a test to measure blood sugar levels in response to a meal and the amount of glucagon that is produced in response to changes in blood sugar. Prior to the test, a catheter will be placed to reduce the number of needle sticks during the test. Subjects will drink 240 ml of a high protein nutrition drink (BOOST). An appropriate amount of insulin for the carbohydrate intake of the meal challenge will be administered via insulin pump to taking the drink. Blood will drawn once before the meal and 8 times during the meal over 3 hours. The total amount of blood that will be drawn is ~ 20 teaspoons (100 mL).

The following parameters will be drawn for measurement during the MMTT

- Blood Glucose
- Glucagon
- Serum inflammatory mediators

Blood samples (5 ml each) will be collected into fluoride (grey top) for glucose measurement and serum separator tubes for serum samples. Glucose levels will be transported to the Kaleida Health Department of Pathology and Laboratory Medicine for analysis. Samples for glucagon and serum inflammatory markers will be kept at room temperature prior to centrifugation. Centrifugation will occur within one to two hours after collection of the samples. The blood samples will be centrifuged for ten minutes at room temperature at a relative centrifugal force of 1500xg. Serum samples will be aliquoted and frozen at -

20°C. All samples will be labeled with subject name, date of birth, subject number, date of collection, and time of collection. Subject number will be assigned sequentially based on entry into the study. All relevant data regarding the samples will be entered into a computer database. Sample assays will be performed in duplicate to control for intra-assay variability.

*8.3 Describe procedures performed to lessen the probability or magnitude of risks.*

Response: All study tasks will be performed in a quiet and private room. Subjects will be advised of potential adverse events and provided with contact information for [name]. Insulin doses will be lowered in order to decrease the risk of hypoglycemia during the liraglutide treatment week.

*8.4 Describe all drugs and devices used in the research and the purpose of their use, and their regulatory approval status.*

Response: Study drug = liraglutide, a GLP-1 analogue. This drug is approved for management of Type 2 diabetes in adults. The liraglutide pen device will be returned following completion of the study, and any remaining drug will be destroyed at the study site by the study investigators. The principal investigators will be responsible for ensuring that the liraglutide devices will only be used by individuals who have provided consent and who have agreed to participate in the study. See attached FDA IND exemption for this study.

*8.5 Describe the source records that will be used to collect data about subjects. (Attach all surveys, scripts, and data collection forms.)*

Response:

A data collection tool (attached) will be used to collect the following data from the patient or from the medical record:

- Age (Year-months; based on date of birth)
- Sex
- Date of diabetes diagnosis
- Insurance Type
- Height (cm) and weight (kg)
- Body mass index (BMI)
- Blood pressure
- Hemoglobin A1c (POS)
- Insulin regimen and daily insulin use
- Other medications
- Side effect diary
- 4 day food records

In addition, the insulin pump download and blood glucose monitor downloads will be reviewed to collect the following information:

For all subjects:

- Number of blood sugar checks/day (average of 7 days prior to visit)
- Total basal dose
- Total daily insulin dose
- %basal/%bolus
- Boluses recorded/day
- Grams of carbohydrate recorded/day

Data will be recorded on the source document that carries the subject identifier number. Data will then be transferred to an Excel spreadsheet – no identifying data will be recorded in this spreadsheet.

*8.6 What data will be collected including long-term follow-up.*

*Response:* See above.

*8.7 For HUD uses provide a description of the device, a summary of how you propose to use the device, including a description of any screening procedures, the HUD procedure, and any patient follow-up visits, tests or procedures.*

*Response:* N/A

